3.17 Analysis of the Pharmacokinetic/Pharmacodynamics Endpoints

Pharmacodynamic Endpoints:

Values for AA, DHA and AA/DHA ratio as well as their change relative to baseline will be tabulated by time point and descriptive statistics will be used. The rate (frequency) of normalization (normalization meaning a parameter value reaching the mean parameter value observed in healthy controls ± 1 Standard Deviation) for AA, DHA, and the AA/DHA ratio will be calculated for the end-of-treatment cycle values, and the treatments will be compared using two-sided multivariate logistic regression with the respective baseline value as a covariate. Alternative methods will be used if necessary due to the data distribution. Healthy controls will consist of a group of approximately 20 healthy, non-CF adult subjects of both genders, not specifically matched to the APPLAUD CF patients.

Values for pharmacodynamic parameters (AA, DHA and AA/DHA ratio), EPA, inflammation markers, metabolipidomic markers, systemic bone formation/resorption markers, markers of oxidative stress, ceramides), as measured in plasma (or serum, or blood, as required), as well as their change relative to baseline, will be tabulated by time point and descriptive statistics will be used. An analysis of variance will be used to compare treatments assuming datasets meet standard pre-requisites for such analysis (normal or log-normal distribution and homogeneity of variance). Alternative methods will be used if necessary.

Pharmacokinetic Endpoints:

Blood samples for fenretinide C_{\min} analysis will be obtained from all patients randomized to fenretinide. Patients randomized to placebo will provide samples (to maintain the study blind) but will not contribute to the C_{\min} data.

Plasma fenretinide C_{\min} concentrations will be presented in a tabular summary, by sampling day and compared between groups of CF patients receiving fenretinide grouped according to the a-priori stratification factors, and assuming stratum size will allow such comparison.

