9.2.2 Baseline and First Dosing Visit (Visit 2, Day 1)

1. Eligible CF patients will be invited to the study site for the baseline procedures and first dosing. This visit must be within 28 days of screening otherwise all or a part of expired screening procedures will need to be repeated/updated (see Section 9.2.1.2);
2. Confirmation of continued eligibility by verification of the inclusion/exclusion criteria, review of the results of the screening safety laboratory tests including plasma retinol and retinol-binding protein, performance of baseline vital signs, urine pregnancy test for women, and focused physical examination;

3. Pulmonary function tests (FEV₁). The actual baseline FEV₁ value for the study will be the average of the screening's best value and the best value obtained during the baseline visit as long as the screening and baseline FEV₁ values are within 15% of each other. A higher difference in FEV₁ % predicted indicates a lack of acceptable pulmonary function stability and the patient should not be randomized on study;
4. Body weight, with BMI calculated;
5. At sites that participates in the bone density exploratory assessment, the first 24 patients who consent to the additional procedure of measuring bone density prior to and after the study treatment, will undergo their baseline assessment; being not exclusionary, this test may be scheduled within a few days of first dose but not after;
6. Baseline Quality of Life questionnaire will be filled out (CFQ-R);
7. At select sites participating in the investigation of the Matouk Disease Score, the Baseline Score will be determined;
8. Pre-dose blood sampling and urine collection for baseline safety laboratory tests, pregnancy test if applicable, plasma retinol and retinol-binding protein, lipidomic tests, ceramides, metabolipidomic tests, systemic bone formation/resorption markers, inflammation and oxidative stress markers;
9. All eligible patients will be stratified according to 1- Baseline FEV₁, 2- PEx number in the prior year, and 3- Co-administration of Kalydeco® (ivacaftor), Orkambi® (ivacaftor/lumacaftor), Symdeko® (ivacaftor/tezacaftor) or another commercially available CFTR modulator product, and equally allocated/randomized to either a daily dose of 300mg of LAU-7b, (as 3 x 100 mg oral hard gelatin capsules), or matching placebo.

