3.14 Analysis of the Primary Efficacy Endpoints

The study will be considered successful if a statistically significant advantage for fenretinide over placebo is obtained for the absolute change in FEV₁ percent predicted from baseline to Week 24, as assessed in the ITT population. Confirmatory analyses will be conducted in the PP Population, Protocol-defined PEx Population and Overall PEx Population.

Values for percent predicted FEV₁ as well as their change relative to baseline will be tabulated by time point and descriptive statistics will be used. In the analysis of the primary efficacy endpoint, the absolute change from Baseline in FEV₁ percent predicted, including all measurements up to Week 28 (both during and after treatment measurements, including after treatment discontinuation) will be analyzed based on a mixed model for repeated measures, with the following specifications:

- The dependent variables will be all the absolute changes in FEV₁ percent predicted from Baseline to each time point, including Week 28;
- The fixed effects will be the treatment group, the visit and the treatment-by-visit interaction;
- The random effect will be the patient;
- An unstructured variance-covariance structure will be adopted as the default structure; alternate variance-covariance structures may be adopted as appropriate.
- The model will be adjusted for the following *à priori* stratification categories:
 - FEV₁ percent predicted determined at Baseline (<70% versus ≥70% predicted),
 - PEx frequency in the prior year (≤3 versus > 3 PEx episodes),
 - Co-administration or not of Kalydeco® (ivacaftor), Orkambi® (ivacaftor/lumacaftor), Symdeko® (ivacaftor/tezacaftor) or another commercially available CFTR modulator product (yes versus no);

- The difference between treatment means at each time point and its 95% confidence interval will be estimated.
- Stratum-specific estimates based on Least Square Means will be generated

The primary result obtained from the model will be the treatment effect at Week 24. The estimated mean treatment effect, a 95% confidence interval, and a 2-sided p-value will be generated.

The analysis will be repeated with the addition of the following covariates in the model:

- Baseline use of Trikafta (yes versus no);
- Effect of the pandemic confinement (pre versus post pandemic onset) (described in Section 3.14.1)

Alternative methods will be used if necessary due to data not meeting the standard requirements for the proposed analysis.

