- Body weight and BMI changes from Baseline/Screening will be summarized using descriptive statistics by treatment group and compared between treatments using a linear mixed model similar to what is described under [Section 3.14](#), with the addition of the baseline parameter (Weight or BMI at baseline) as covariate in the model.

Quality of Life Endpoints:

- Quality-of-life data will be derived from the questionnaires according to the corresponding scoring manuals and will be summarized by treatment group. Patients' health state will be derived from the CFQ-R questionnaire, including the extracted CFQ-R respiratory domain, a separate endpoint. Additional exploratory health condition will be evaluated by the Matouk Disease Score. Data will be summarized by treatment group using descriptive statistics.

Analysis of the absolute change from baseline for the CFQ-R (overall and respiratory domain) as well as the Matouk Disease Score will be performed similarly to that of the primary efficacy endpoint with the addition of the CFQ-R score at baseline as a covariate for the analysis of the CFQ-R variables.

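### The continuous pharmacodynamic markers are compared by an analysis of variance with no named baseline covariate, stratification factor or outcome scale; baseline-adjusted ANCOVA would be at least as precise at little cost

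*SAP*

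**What the plan says.** SAP 3.17 covers the continuous AA, DHA, AA/DHA and EPA values and the inflammation, metabolipidomic, bone, oxidative-stress and ceramide markers. On the treatment comparison it says: "An analysis of variance will be used to compare treatments assuming datasets meet standard pre-requisites for such analysis". The prerequisites it names are normality or log-normality, and equal variances. It then adds: "Alternative methods will be used if necessary". For AA, DHA and their ratio, values "as well as their change relative to baseline will be tabulated by time point and descriptive statistics will be used"; the paragraph on the wider marker list has nearly the same wording. Neither paragraph says which of the two, value or change, goes into the ANOVA. Protocol 12.4.2 specifies the same method with the same gaps.

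Baseline data exist. Protocol 9.2.2 schedules pre-dose Day 1 samples for "lipidomic tests, ceramides, metabolipidomic tests, systemic bone formation/resorption markers, inflammation and oxidative stress markers".

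Elsewhere the SAP does adjust:

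- Lipid normalization (3.17): "the treatments will be compared using two-sided multivariate logistic regression with the respective baseline value as a covariate".
- Weight and BMI (3.15): a mixed model like the primary one, "with the addition of the baseline parameter (Weight or BMI at baseline) as covariate in the model".
- CFQ-R (3.15): the primary-type model, "with the addition of the CFQ-R score at baseline as a covariate for the analysis of the CFQ-R variables". The Matouk score is covered by the same sentence but receives no baseline Matouk term.
- FEV1 (3.14): "The model will be adjusted for the following" stratification categories, of which there are three.

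**The concern.** The systemic inflammation markers are a secondary endpoint and bear directly on the proposed anti-inflammatory mechanism. The other continuous markers are exploratory. SAP 3.2 tests everything beyond the primary analysis at a nominal 5%, mainly for signal detection, so avoidable noise works against the stated purpose. Protocol section 6 reports that in the Phase Ib study variability prevented firm conclusions on most of these measures.

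There is also a pre-specification gap. The outcome scale and covariates are open and the fallback is undefined, so the analyst could choose among several models after seeing the data.

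**Working it through.** **Inputs.** The documents give no standard deviation, correlation, effect size or sample size for any marker, so there is no plan figure to reproduce. The correlation r between baseline and follow-up is therefore an assumption, shown over 0 to 0.9. The group size of 60 completers comes from the FEV1 calculation (SAP 2.6) and serves only as an illustration. Tests are two-sided at 5% (SAP 3.1.1).

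**Formulas.** Let s be the common SD at baseline and follow-up. Per-patient variance of the quantity compared:

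- follow-up value: s²
- change: 2(1-r)s²
- ANCOVA: (1-r²)s²

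Against a change-score ANOVA the ratio is (1-r²)/[2(1-r)] = (1+r)/2, so ANCOVA removes (1-r)/2 of the variance. Against a follow-up-value ANOVA it removes r². The reduction in standard error is 1 minus the square root of the variance ratio.

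| r (assumed) | Variance cut vs change | SE cut vs change | Variance cut vs follow-up value | SE cut vs follow-up value |
|---|---|---|---|---|
| 0 | 50% | 29% | 0% | 0% |
| 0.3 | 35% | 19% | 9% | 5% |
| 0.5 | 25% | 13% | 25% | 13% |
| 0.6 | 20% | 11% | 36% | 20% |
| 0.8 | 10% | 5% | 64% | 40% |
| 0.9 | 5% | 2.5% | 81% | 56% |

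The two readings move in opposite directions as r rises, so the gain cannot be stated without knowing which variable is tested. A simulation with 60 per group and 4,000 runs at r = 0.3, 0.45 and 0.6 agreed with the formulas to within 3 percentage points.

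**Power.** Take the effect that ANCOVA detects with 80% power at 60 per group, which is (1.960 + 0.842) × √[(1-r²) × 2/60] in units of s. By the normal approximation the alternatives have:

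- r = 0.3: change-score ANOVA 62%, follow-up-value ANOVA 76%
- r = 0.6: change-score ANOVA 71%, follow-up-value ANOVA 61%
- r = 0.8: change-score ANOVA 76%, follow-up-value ANOVA 39%

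**Sampling days.** Inflammation and oxidative-stress markers are taken on Days 1, 21 and 161 (Protocol 10.3, 10.8.4), and ceramides and metabolipidomics on the same days (Schedule of Events). Lipids are taken on Days 1, 21, 161 and 189 (10.2), and bone markers on Days 1 and 161 only (10.8.3). A repeated-measures model is therefore possible for all families except bone.

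**Degrees of freedom.** One baseline term and three two-level factors use 4 degrees of freedom. With 120 completers the residual falls from 118 to 114.

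**The case against.** Several objections have force.

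- A reader might infer that baseline is ignored altogether. The documents do not support that. The endpoints in SAP 2.8.1 are worded mostly as changes from the pre-study value, and a change score uses baseline by subtraction. The lipid-normalization endpoint is also already baseline-adjusted. What is missing is a baseline covariate in the continuous comparisons.
- A reader might infer that a fixed 20-35% of precision is wasted. That range is a variance reduction, and it holds only for a change-score ANOVA with r between 0.3 and 0.6. SAP 3.17 states neither condition. In standard-error terms it is 11-19%, and it shrinks as r rises.
- A reader might infer that the ANOVA has treatment as its only term. The text does not say so, and it allows alternatives. Underspecification is the fair description.
- A reader might infer that omitting the strata necessarily inflates the standard errors. That follows only if the strata predict the marker, and the documents give no figure for this.
- SAP 3.15 bases secondary efficacy analyses on Week 24, so a target time arguably exists for the inflammation markers. SAP 3.17 also already contemplates log-normal data. Logging every marker regardless would change the effect measure, so it should not be a blanket rule.
- The Matouk score is exploratory and collected at selected sites. Its model already includes FEV1 category and prior exacerbations, which overlap parts of the score. The figures above do not apply to it.

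These points narrow the claim but leave the gap in 3.17. The permission for unspecified alternatives does not fill it.

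**Conclusion.** The point holds as an inexpensive improvement to secondary and exploratory analyses. SAP 3.17 leaves the covariates and the tested variable open, although Day 1 values are collected and sister analyses in the same SAP use them. In a randomised comparison with equal variances, ANCOVA is asymptotically never less precise than either form of ANOVA. The gain vanishes only as r approaches 1 (change analysed) or 0 (follow-up value analysed).

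For an assumed r of 0.3 to 0.6, the variance falls by 35% to 20% against change scores (standard error by 19% to 11%), or by 9% to 36% against follow-up values. These sizes rest on an r that the documents do not give and on equal SDs at baseline and follow-up. Nothing is claimed for the strata beyond consistency with the stratified design. The FEV1 analysis and the criterion for study success are untouched.

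**What to change.** In SAP 3.17, replace the ANOVA by ANCOVA with treatment, the baseline value of the same marker, and the three randomisation factors. With outcome and baseline on the same scale, the treatment estimate is identical whether the value or the change is modelled, so this also settles the open question of which is tested.

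- Use the log scale for markers that are log-normal and report geometric-mean ratios; keep the original scale for the others.
- Name Week 24 (Day 161) as the main time point.
- Use a repeated-measures version of the model where there are two or more post-baseline samples. Bone markers keep the single-time-point ANCOVA.
- As a minor addition, put the baseline Matouk score, which is collected on Day 1, into the Matouk model in SAP 3.15.
- Record the departure from Protocol 12.4.2 in SAP section 5.

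The cost is SAP wording, minor programming, about 4 degrees of freedom, and a ratio instead of a mean difference for the logged markers. No new data are needed.

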3.18 Analysis of the Safety Endpoints

For the purpose of analyses and tabulations, AEs will be classified as pretreatment AEs, TEAEs, or posttreatment AEs. More specifically: Pretreatment AE are those that started before the first dose of study drug. TEAE are those that increased in severity or appeared at or after the first dose of study drug and before or at the last follow-up, planned for 4 weeks after the last dose of study

drug. Post-treatment AEs are those that increased in severity or that appeared after the last follow-up, planned for 4 weeks after the last dose of study drug; these AEs will be reported by the Investigator to the sponsor and the appropriate regulatory agency, as well as treated and followed according to local regulations. Post-treatment AE's will be reported separately from the study's clinical study report.

For AEs with missing or incomplete start dates, if there is no clear evidence that the AEs started before or after the first dose of study drug, then the AEs will be classified as TEAEs.

TEAEs will be coded using the Medical Dictionary for Regulatory Activities (MedDRA) and the following information will be summarized:

- Overall TEAEs will also be described according to:
 - Seriousness (yes, no),
 - Severity (mild, moderate, severe, life-threatening),
 - Causality (definitely related, probably related, possibly related, not related),
 - Action taken with study drug (dose not changed, dose interrupted, drug withdrawn, not applicable),
 - Outcome (recovered / resolved, recovered / resolved with sequelae, not recovered / resolved, fatal, unknown).
- The total number of TEAEs, the total number and proportion of patients experiencing at least one TEAE during the treatment period will be summarized by system organ class (SOC) and preferred term (PT). TEAEs occurring with an incidence $\geq 10\%$ will be tabulated in a separate table. To count the number of patients who experience each TEAE, patients experiencing the same TEAE multiple times will only be counted once for the corresponding PT. TEAEs will be tabulated presenting the SOCs alphabetically. All TEAEs, and TEAEs occurring with an incidence $\geq 10\%$, will be presented overall as well as stratified by causality (Definitely Related, Probably Related, Possibly Related, Not Related).
- AE summary tables will be presented for TEAEs only and will include the following:
 - All TEAEs;

- TEAEs by relationship;
- TEAEs by maximal severity;
- TEAEs leading to treatment discontinuation;
- Serious TEAEs;
- Fatal TEAEs.

All safety analyses will be performed on the Safety population.

Additional Safety Evaluations

The following safety evaluations, listed below, will be performed per the methodology stipulated in each of the respective sections provided:

- Clinically relevant changes from baseline in vital signs (for more details, please see Section 3.7);
- Clinically relevant changes from screening in 12-lead ECG (for more details, please see Section 3.7);
- Clinically relevant changes from baseline in physical examinations (for more details, please see Section 3.7);
- Clinically relevant changes from baseline in safety laboratory assessments (hematology with differential count, biochemistry, and urinalysis) (for more details, please see Section 3.8);
- Plasma retinol and retinol-binding protein values, changes from screening/baseline, correlated with ophthalmological symptoms, specifically symptoms of nyctalopia. More precisely, Spearman correlation between plasma retinol and retinol-binding protein concentrations (change-from-baseline to Week 24) and the cumulative number of AEs for “nyctalopia” will be presented in scatter plot figures along with the regression line. Nyctalopia will be identified according to AEs of the following SOC/PT/LLT: Eye disorders/ Night blindness/ Nyctalopia.
- Change in PEx incidence and antibiotic treatment requirement (for more details, please see Section 3.14).

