5.4.5 Specific Rationales for this Phase II study

5.4.5.1 Design/Structure

This is a randomized, double-blind (patients, Investigators and blinded study staff), placebo controlled, Phase II study (details are presented in Section 7.2). There will be no active control treatment but patients will undergo the Standard of Care at their institution. A randomized, double-blind study design will avoid observer bias and reduce symptoms or outcomes arising from the patients' knowledge of treatment. A parallel design will better detect treatment effects and is appropriate for this phase of development.

A Phase Ib study with fenretinide was conducted recently in adult CF patients. The safety results show that LAU-7b is well tolerated over 3 x 21-days cycles of progressively increasing oral doses up to 300 mg/day. The anticipated duration of treatment in the Phase II study is 6 cycles of 21 days, totalling around 24 weeks. Compared to the Phase Ib study, this duration of treatment will permit all safety and efficacy variables to be measured for an additional 3 months to obtain a more robust assessment that is less affected by short-term variability and influence of PEx.

The 24-weeks duration is anticipated to facilitate detection of significant changes in the primary efficacy endpoint FEV₁, and to also help determine the impact of fenretinide on secondary efficacy variables such as the PEx-related variables, weight and BMI, bone density, systemic bone formation/resorption markers as well as the Quality of Life assessments. While it is anticipated that the effect on the lipidomic and inflammation biomarkers endpoints will appear rapidly after the start of treatment, a 24-weeks duration will allow for an assessment of the durability of response for all parameters. The follow-up period of approximately one month after the last dose is deemed adequate for assessing safety, biomarkers and efficacy, because fenretinide and its metabolites are expected to reach undetectable levels within 7-10 days after the last dose. Thus, the follow-up period will be mostly on a drug free background. This period will also enable assessment of whether some effects on pharmacodynamic markers last longer than the drug systemic presence. The study also aims at gathering efficacy and additional safety information about LAU-7b in CF patients.

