8.4 Treatment Discontinuations

Patients should discontinue treatment with the study treatment, but remain on the study for adequate follow-up, for any of the following reasons:

- Patients may discontinue study drug treatment at any time if the patient, Investigator, or Laurent determines that it is not in the best interest of the subject to continue treatment.
- Unacceptable toxicity associated with treatment (see below stopping rule, section 8.4.1)
- Clinically significant lab abnormalities or adverse events that, in the Investigator's judgment, would preclude continued treatment.

The reason for treatment discontinuation will be noted on the e-CRF.

If a patient discontinues treatment due to unacceptable toxicity or any other safety reason, that patient should either continue to be assessed according to the planned visit schedule for safety and for relevant efficacy parameters, or at the minimum, attend a Treatment Discontinuation Visit four (4) weeks after having received the last dose of study drug.

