11.1.1 Documentation of Adverse Events

Adverse events will be collected from the time of informed consent until the last scheduled study follow-up, 4 weeks after the last dose of the study drug, or until the last unscheduled safety-related assessment whichever occurs latest. An AE is any untoward medical occurrence (which does not necessarily have to have a causal relationship with this treatment). An AE can be any unfavorable and unintended sign (including an abnormal laboratory finding, for example), symptom, or disease temporally associated with the use of an investigational product, whether or not related to the study drug. This includes any occurrence that was new in onset or aggravated in severity or frequency from the baseline condition. Planned hospital admissions or surgical procedures for an illness or disease that existed before the patient was screened in the study are **not** to be considered AEs unless the condition deteriorated in an unexpected manner during the study (e.g. surgery was performed earlier than planned).

Abnormal results of diagnostic procedures, including laboratory test abnormalities, are considered AEs if they result in any one of the following:

- Discontinuation of study treatment;
- Require treatment or any other therapeutic intervention;
- The necessity for further diagnostic evaluation (excluding a repetition of the same procedure to confirm the abnormality);
- Association with clinical signs or symptoms that may have a significant clinical impact, as determined by the Investigator.

Patients are encouraged to report AEs spontaneously or in response to general, non-directed questioning. All AEs are to be followed until resolution or until a stable clinical endpoint is reached. The investigator should question patients about AEs and changes in pre-existing illnesses since their last visit and must record the information in the patients' medical records. The onset and end dates, severity, relationship to study agent, action taken, and outcome must be recorded for each AE. All AEs are to be recorded on the appropriate e-CRF and in detail on the source documents.

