Any AE that occurs within 4 weeks following the last dose of the study drug will be considered treatment emergent (TEAe) and must be recorded in the e-CRF and, if an SAE, reported immediately to the Sponsor. Adverse events that are ongoing at the end of the 4-week follow-up period should be marked as ongoing. However, it is the responsibility of the Investigator to follow up on these events until resolution, according to standard medical care.

Any AE or SAE that the investigator becomes aware of outside of the reporting period until the end of the study that has or is believed to have a causal relationship to the study drug should be reported to Laurent

Pharmaceuticals via telephone. Patients who experience AEs will be monitored with relevant clinical assessments and laboratory tests, as determined by the Investigator. All AEs and laboratory abnormalities encountered during the study should be followed until resolution or stabilization of the event(s). Any action taken and follow-up results must be recorded in the patient's medical record. Follow-up laboratory results should be filed with the patient's source documentation and e-CRF. For all AEs that require the patient to discontinue treatment, relevant clinical assessments and laboratory tests should be repeated on at least a monthly basis until final resolution or stabilization of the event(s). These assessments should be captured in the source data and SAE forms but will not be entered in the e-CRF.

All AEs for randomized patients will be recorded in the e-CRF and the patient's source documents. AEs for patients who are screened but not subsequently randomized in the study will be recorded only in the patient's source documents. The following data should be documented for each AE:

- Description of the event;
- Classification of "serious" or "not serious";
- Date of first occurrence and date of resolution (if applicable);
- Severity;
- Causal relationship to study drug(s);
- Action taken;
- Outcome;
- Concomitant medication or other treatment given

An independent DSMB will assess AEs that are reported from study sites. The DSMB will meet at regular intervals throughout the duration of the study or will meet as determined by the DSMB chair, and may recommend systematic treatment arm dose reduction or early termination of the study for safety reasons (see Sections 7.2.4 and 7.2.2).

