12.5.1 Adverse Events

Adverse events will be tabulated with reported incidences by treatment, number of patients that presented adverse events by treatment, serious adverse events by treatment, number of adverse events by body system and by treatment. Summaries will be presented by MedDRA system organ class and preferred term.

For the purpose of analyses and tabulations, AEs will be classified as pretreatment AEs, TEAEs, or post-treatment AEs. More specifically: Pretreatment AE are those that started before the first dose of study drug. TEAE are those that increased in severity or that was appeared at or after the first dose of study drug and before or at the last follow-up, planned for 4 weeks after the last dose of study drug. Post-treatment AEs are those that increased in severity or that appeared after the last follow-up, planned for 4 weeks after the last dose of study drug. For AEs with missing or incomplete start dates, if there is no clear evidence that the AEs started before or after the first dose of study drug, then the AEs will be classified as TEAEs.

AE summary tables will be presented for TEAE only and will include the following: All TEAEs, TEAEs by relationship, TEAEs by maximal severity, TEAEs leading to treatment discontinuation, Serious TEAEs and fatal TEAEs. All AEs, including pre-and post-treatment AEs, will be presented in individual patient data listings.

The number and percentage of patients with at least one AE, as classified by preferred term and system organ class, will be summarized for each treatment group. For these summaries, patients with multiple events will be counted only once per preferred term. AEs will also be summarized by severity and relationship to study drug. At each level of summarization, the event with the highest level of severity or strongest drug relationship will be presented.

All AEs must be listed. In addition, detailed listings will be provided for patients who die, experience a SAE, or discontinue the study because of an AE. These listings will include treatment, patient's age, duration of follow-up, amount of fenretinide received, and time since last intake. Patients who develop Grade 3-4 toxicities will also be listed separately.

A Fisher's Exact test will be used in an exploratory sense to evaluate differences between treatment groups in the incidence of treatment-emergent and clinically significant AEs, graded according to CTCAE outlined in Section 11.1.1.1.

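### The treatment-emergent window closes on different dates in Protocol 11.1.1 and in Protocol 12.5.1/SAP 3.18 for patients who stop drug early but stay on study, and the SAP changes how post-treatment AEs are reported without recording it

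*SAP*

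**What the plan says.** **Window.** Protocol 11.1.1 states: "Any AE that occurs within 4 weeks following the last dose of the study drug will be considered treatment emergent (TEAe"). Protocol 12.5.1, which sets the classes used for tabulation, includes events that arise or worsen from first dose and "before or at the last follow-up, planned for 4 weeks after the last dose of study drug". SAP 3.18 repeats this, covering events that worsened or newly "appeared at or after the first dose of study drug and before or at the last follow-up, planned for 4 weeks after" dosing ends.

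**Follow-up after stopping drug.** Protocol 8.4 says of a patient who stops for toxicity or another safety reason: "that patient should either continue to be assessed according to the planned visit schedule for safety and for relevant efficacy parameters". The stated minimum is a single discontinuation visit four weeks after the last dose. The opening of Protocol Section 12 gives early discontinuers in general a similar choice: all scheduled visits, or at least one month of follow-up.

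**AE collection.** Protocol 11.1.1 collects events "until the last scheduled study follow-up, 4 weeks after the last dose of the study drug", or to the last unscheduled safety assessment if that is later.

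**Post-treatment events.** Protocol 12.5.1: "All AEs, including pre-and post-treatment AEs, will be presented in individual patient data listings". SAP 3.18: "Post-treatment AE's will be reported separately from the study's clinical study report".

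**Drug clearance.** Protocol 5.4.5.1: "fenretinide and its metabolites are expected to reach undetectable levels within 7-10 days after the last dose".

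**The concern.** The wording assumes that the last follow-up falls 4 weeks after the last dose. That is true for a completer but need not be true for an early stopper, and no section says which date governs when they part. Read literally, the SAP gives different windows to two patients who stop on the same day if one keeps the visit schedule and the other attends the single visit. That choice is made after randomisation and may be related to toxicity.

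TEAE incidence against placebo is the first primary objective (Protocol Section 6, SAP 2.3.1), and SAP 3.18 describes no adjustment for length of observation. The same window also defines the TEAE period used for the vital-sign and ECG tables (SAP 3.8) and the laboratory shift tables (SAP 3.9). If early stopping differs between arms, so does the amount of off-drug time counted as treatment-emergent.

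The two documents also disagree on whether post-treatment events appear in the clinical study report.

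**Working it through.** **Inputs.** Six cycles of 21 days on and 7 days off (Protocol 9.4). Follow-up visit around Day 189 (Schedule of Events). One dose is enough for the Safety population (Protocol 12.2, SAP 3.3).

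**Reproducing the plan's own date.** The last dosing day of cycle k is 21 + 28(k − 1). For k = 6 this is Day 161, and 161 + 28 = Day 189. This matches the schedule and SAP 2.5, so the rules agree for completers.

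**Gap between the rules.** For a patient whose last dose is on Day L and who stays to Day 189, the 4-week rule closes on Day L + 28 and the last-follow-up rule on Day 189. The gap is 189 − (L + 28) = 161 − L.

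| Last dose (Day L) | 4 weeks after last dose | Last follow-up | Gap (days) |
|---|---|---|---|
| 1 (single dose) | Day 29 | Day 189 | 160 |
| 21 (end of cycle 1) | Day 49 | Day 189 | 140 |
| 49 | Day 77 | Day 189 | 112 |
| 77 | Day 105 | Day 189 | 84 |
| 105 | Day 133 | Day 189 | 56 |
| 133 | Day 161 | Day 189 | 28 |
| 161 (completer) | Day 189 | Day 189 | 0 |

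The maximum is 160 days. For a stopper who attends only the 4-week visit, the last follow-up is itself Day L + 28 and the gap is 0. Visit timing around Day 189 can move these figures by a few days.

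**Off-drug time inside the longer window.** With last dose on Day 21, drug is expected to be undetectable by Day 28 to 31 (21 + 7 to 21 + 10). A window open to Day 189 then covers a further 158 to 161 days (189 − 31 to 189 − 28).

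**Post-treatment events, side by side.** Protocol 12.5.1 puts them in the patient listings; SAP 3.18 reports them apart from the study report. SAP Section 5 records the removal of Fisher's exact test from Protocol 12.5.1 but has no entry for this change, nor for any change to the window.

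**The case against.** The strongest reply is that the analysis text is consistent. Protocol 12.5.1 and SAP 3.18 agree and are written for tabulation. Protocol 11.1.1 sits in the section on recording and reporting; it says that events within 4 weeks are treatment-emergent, not that later ones are not. On that view the analysis definition governs. That is a fair account of precedence, but it does not remove the dependence on the follow-up option, and the reference to a planned 4 weeks still leaves an analyst two possible dates.

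A second reply is that following patients to the last visit regardless of dosing suits the primary FEV1 analysis, which keeps measurements after discontinuation. A cut-off tied to the last dose makes windows shorter for every early stopper: 49 days for a stop at Day 21, against 189 for a completer. This stands as a real trade-off, and it is why the fix needs a second table.

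Third, no formal inference is at risk. Success rests on FEV1 alone (SAP 3.2 and 3.14), and SAP Section 5 makes the AE comparison descriptive. This stands.

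Three stronger readings are tempting but unsupported:

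- A reader might infer a large swing in the proportion of patients with at least one TEAE. A patient who stops for safety will normally already have an event and be counted under either window. Patients who stop for other reasons could change that proportion, but the documents give no basis for saying by how much.
- A reader might apply the 10% drop-out allowance to the 136 randomised patients to count those affected. That allowance concerns leaving the study; the rules diverge only for patients who stop drug and remain, and Protocol Section 12 separates the two.
- A reader might infer that later AEs and SAEs of early stoppers vanish from the report. As written, post-treatment events are those after the last follow-up, so on-study events stay in. That loss would arise only if the cut-off were read as 4 weeks after last dose while the SAP's reporting sentence stayed. Even then, SAP 3.18 keeps reporting to the sponsor and regulator.

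**Conclusion.** The point holds as an inconsistency in a safety definition that should be settled before unblinding. For early stoppers who stay on schedule, the two cut-offs differ by 161 minus the last-dose day, up to 160 days. As written, the SAP window depends on a post-randomisation follow-up choice and can label events months after expected clearance as treatment-emergent. What can move are event counts, preferred-term rates and the laboratory, vital-sign and ECG tables that use the TEAE period. The gap rests only on the documents' calendar and on the patient attending Day 189. The effect on TEAE incidence cannot be computed, because the documents do not give the number of such patients.

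The unrecorded change in reporting post-treatment events is a separate, smaller defect and stands on either reading of the window. The mock tables of SAP Section 7 were not in the text available for this check, so whether a listing survives there is unverified.

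**What to change.** 1. Use one definition in Protocol 11.1.1, Protocol 12.5.1 and SAP 3.18: onset or worsening from first dose through 28 days after the patient's own last dose. Apply it wherever the TEAE period is used.
2. Keep collecting AEs and SAEs to the last study visit for everyone still followed. Align the collection wording in Protocol 11.1.1, which carries the same double date and limits later reporting to events believed related to the drug.
3. Tabulate later on-study events by arm as off-treatment. Totals to last visit can then also be read, and the shorter window for early stoppers is visible.
4. Restore the listing of post-treatment AEs in the clinical study report, or record the change with its reason in SAP Section 5. Make this change together with item 1; otherwise the new cut-off could send on-study events outside the report.

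The cost is wording in both documents and one extra table. TEAE counts may be slightly lower, with the difference shown in the off-treatment table; no data are lost.
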